PROTOCOL AMENDMENT #5

LCCC 1128: Open Label Phase II Trial of the BRAF inhibitor (Dabrafenib) and the MEK inhibitor (Trametinib) in Unresectable Stage III and Stage IV BRAF Mutant Melanoma; Correlation of Resistance with the Kinome and Functional Mutations

AMENDMENT INCORPORATES (check all that apply):

- Editorial, administrative changes
 Scientific changes (IRB approval)
 Eligibility Changes (IRB approval)

The purpose of this amendment is to allow the collection of progression biopsies from subjects who are withdrawn from the LCCC 1128 study for a variety of reasons including, but not limited to, a lack of tolerability, need to receive other therapy or completion of 3-years of study treatment without progression. The subset of the aforementioned subjects who are later re-challenged with dabrafenib and trametinib combination therapy and then progress while on this treatment, may be biopsied at the time of their clinical or radiological progression. These subjects are required to consent to this biopsy collection prior to being placed back on the LCCC 1128 clinical trial. Previously in protocol amendment #3, subjects who were withdrawn from study treatment due to an inability to tolerate the combination regimen, but who continued on BRAF inhibitor targeted therapy, were able to be consented, at the time of progression from single agent therapy, to undergo the a progression biopsy. As the protocol's objectives focus on combination therapy, the protocol is also currently being amended to remove this scenario. No subjects were biopsied who progressed solely on single agent therapy and thus this amendment will not affect previously collected data.

The following modifications were made to this protocol for amendment #5:

Editorial, Administrative Changes:

- Minor spelling grammar and formatting changes throughout the protocol
- Removal of Co-Investigators from the Face Page of the protocol
- Addition of the IND # to the Face Page of the Protocol
- IRB Reporting Requirements were updated in accordance with the UNC IRB SOPs (Section 7.3.3)
- FDA Expedited Reporting language was updated to better capture FDA guidance provided in 21CFR312.32 (IND Safety Reporting) (Section 7.3.3)
- Required documentation (Section 9.2) was updated to include financial disclosures
- Single Patient/Subject Exceptions (Section 9.5.2) was updated in accordance with Lineberger Comprehensive Cancer Center's Single Subject Exceptions Policy.

Scientific Changes:

- Updated the study synopsis, study schema, biopsy section, Time and Events Table and correlative study procedures to indicate that former LCCC 1128 subjects who

- progress on standard of care dabrafenib/trametinib off study are eligible for a progression biopsy (Section 1.1, 4.1, 4.2, 4.7, 6.1 and 6.7)
- The biopsy, duration of follow-up, Time and Events Table and follow-up assessments sections of the protocol were updated to indicate that subjects who are placed back on study for the purposes of a progression biopsy will remain on study for safety monitoring, in relation to the biopsy procedure, for 30 days. Subjects who have an ongoing \geq grade 2 or serious AE (SAE) related to the study procedure at 30 days will continue to be followed until the event is resolved or deemed irreversible by the investigator (Section 4.2, 4.7, 6.1 and 6.5).
 - The assessment of primary endpoint and efficacy section (Section 6.9) was updated to clarify that analysis of progression biopsies from subjects placed back on study after progressing on standard of care dabrafenib/trametinib will be included in the analysis of the primary and correlative secondary objectives.
 - The section on sample size and data analysis plans was updated to clarify that tumor samples from patients who progress on study and those who are removed from study and later progress on the combination treatment will be analyzed as one data set (Section 8.1).

Eligibility Criteria:

- Addition of inclusion criteria for off-study subjects who may be consented to come back on study for the purposes of a progression biopsy when they progress on standard of care dabrafenib and trametinib treatment (Section 3.3).
 - Subjects must have currently progressed while receiving trametinib and dabrafenib combination therapy.
 - Subjects must be willing to undergo a research biopsy
 - Subjects must have a tumor amenable to research biopsy
 - Subjects must provide informed consent
 - Subject must have been previously enrolled on the LCCC 1128 protocol.

THE ATTACHED VERSION DATED NOVEMBER 22, 2017 INCORPORATES THE ABOVE REVISIONS

PROTOCOL AMENDMENT #4

LCCC 1128: Open Label Phase II Trial of the BRAF inhibitor (Dabrafenib) and the MEK inhibitor (Trametinib) in Unresectable Stage III and Stage IV BRAF Mutant Melanoma; Correlation of Resistance with the Kinome and Functional Mutations

AMENDMENT INCORPORATES (check all that apply):

- Editorial, administrative changes
 Scientific changes (IRB approval)
 Eligibility Changes (IRB approval)

The following modifications were made to this protocol for amendment #4:

- 1) This amendment adds a requirement for annual ophthalmic exams while on treatment (see section 6.3.4 and time and events table)
- 2) Clarification of the duration follow-up period (see section 4.7 and 6.6). Regardless, of the reason that a patient comes off treatment, dermatologic exams will continue every 3 months for the first 6 months following discontinuation from dabrafenib, and may be done by a physician local to the patient. Only after these dermatologic exams are complete is the patient considered off follow-up, even if they do not require survival follow-up for this entire 6 month period.
- 3) This protocol amendment also clarifies that whether or not a subject enrolls in LCCC 1108, they will be asked to provide a single blood sample (approximately 8 mL) for research purposes. This blood sample may be collected at any point in the study, including during follow-up.
- 4) Section 7.3.3 has been updated with the new language in regards to Novartis reporting requirements.
- 5) [name], [name], and [name] have been added as co-investigators to the protocol title page
- 6) A line to provide the version of the protocol was added to the protocol signature page

In addition, the summary of changes for amendment #3 states that the sponsor changed from GSK to Novartis. Novartis is the funding source for this study and not the sponsor. No changes were made in protocol amendment #4 based on this clarification.

THE ATTACHED VERSION DATED AUGUST 1, 2016 INCORPORATES THE ABOVE REVISIONS

PROTOCOL AMENDMENT #3

LCCC 1128: Open Label Phase II Trial of the BRAF inhibitor (Dabrafenib) and the MEK inhibitor (Trametinib) in Unresectable Stage III and Stage IV BRAF Mutant Melanoma; Correlation of Resistance with the Kinome and Functional Mutations

AMENDMENT INCORPORATES (check all that apply):

- X_ Editorial, administrative changes
- X_ Scientific changes (IRB approval)
- X_ Eligibility Changes (IRB approval)

The following modifications were made to this protocol for amendment #3:
Eligibility criteria were modified to refine the definition of hypertension in exclusion criterion 3.2.6

- 1) At progression biopsy wording was changed to allow for attainment of biopsies in subjects withdrawn from study treatment due to lack of tolerability of the combination regimen and continued on BRAF inhibitor targeted therapy. These subjects should be re-consented so that progression biopsy can be obtained at the time of relapse on BRAF inhibitor targeted therapy (i.e., dabrafenib or vemurafenib). (Sections 4.2 and 6.7 and footnote #11 to Time and Events Table in section 6.1)
- 2) The frequency of tumor assessment scans was reduced to every 12 weeks for subjects responding to combination therapy after cycle 9

AND

- The frequency of tumor assessment scans was reduced to every 6 months for subjects responding to combination therapy for > 2 years (Section 6.3.2 and footnote b added to Time and Events Table in Section 6.1)
- 3) The frequency of ophthalmic exams was reduced and are now only required at Screening and as clinically-indicated due to the presence of ocular symptoms (Section 6.3.2 and Time and Events Table in Section 6.1)
 - 4) Sponsor changed from GlaxoSmithKline to Novartis
 - 5) Blood Sample:
For those patients who do not co-enroll into LCCC1108, we will ask for a blood sample (~8mLs) to ensure sufficient germline DNA in the event tissue samples are insufficient or request blood samples collected under LCCC9001 with IRB # 90-0573. This change is reflected in section 1.6, section 6.1 footnote #13, and 6.7
 - 6) In anticipation of the pending switch from investigative product to commercial supply by the sponsor the following language was added: Trametinib/Dabrafenib commercially available product with auxiliary labeling will be provided by Novartis. The study drug should be administered and stored as per the instructions specified on the label (refer to the label, the PI or the IB for more detailed information). In addition, MSDS will now be available upon request from Novartis and not GSK (See sections 5.1.1, 5.1.2, 5.2.1, and 5.2.2)
 - 7) Sponsor SAE reporting requirements for GSK were deleted and replaced with SAE reporting requirements for Novartis in section 7.3.3.

THE ATTACHED VERSION DATED SEPTEMBER 15, 2015 INCORPORATES THE ABOVE REVISIONS

PROTOCOL AMENDMENT #2

LCCC 1128: Open Label Phase II Trial of the BRAF inhibitor (Dabrafenib) and the MEK inhibitor (Trametinib) in Unresectable Stage III and Stage IV BRAF Mutant Melanoma; Correlation of Resistance with the Kinome and Functional Mutations

AMENDMENT INCORPORATES (check all that apply):

- X_ Editorial, administrative changes
X_ Scientific changes (IRB approval)
X_ Eligibility Changes (IRB approval)

Minor editorial changes made throughout; changed biostatistician to [name]; Requirement of tissue collection taking place at UNC have been removed as no other sites are involved in this study (sections 1.1, 1.7)

Safety and Efficacy

The 2 medications in the study were FDA approved in combination as of January 2014, and new Investigator Brochures were issued for dabrafenib, trametinib, and the combination. Based on these documents (including the updated package inserts), additional information on safety and efficacy on the combination has been incorporated into the protocol. These changes are reflected in sections 1.3, 1.4, 1.5, 5.1 and 5.2. Common AEs using combination therapy are listed in section 5.2.9. Section 1.7 was updated to include recent data indicating a possible survival benefit if patients are continued on BRAF inhibition post disease progression.

Eligibility

- Clarified that patients with elevated bilirubin due to Gilbert's disease will not be excluded (section 3.1.6)
- Clarified exclusion criteria 3.2.6 to "Patients with history of hypertension should have hypertension adequately controlled (BP < 140/90) with appropriate anti-hypertensive therapy or diet prior to study entry"
- Changed central serous retinopathy to new name: retinal pigment epithelial detachment (RPED) (section 3.2.13; also 1.5; 4.4.3)
- Revised section 3.1.3 to indicate that patients with BRAFV^{600K} are also eligible in addition to BRAFV^{600E}, as the dabrafenib/trametinib combination is FDA approved in both populations.
- Added section 3.1.7 clarifying that prior anti-cancer treatment related toxicities must have resolved prior to enrollment.
- Detailed information added to section 3.1.9 on what constitutes effective contraception, and statement referencing this information added to inclusion criteria 3.1.10.
- Exclusion criteria 3.2.2 added (History of malignancy with confirmed activating RAS mutation at any time. *Note:* Prospective RAS testing is not required. However, if the results of previous RAS testing are known, they must be used in assessing eligibility)
- Minor clarifications added to exclusion criteria 3.2.8, 3.2.11, and 3.2.14

Correlatives

Biopsies

Modified section 4.2 on timing of biopsies and removed statement that biopsy must be 'core' biopsy. (section 6.6 and 6.8) Clarified that biopsies may be delayed beyond point of disease progression if patient remains on therapy. The decision to continue therapy should be based on clinical benefit and safety considerations. Also updated in key to table of time and events (section 6.1, 6.4.1 and 6.7).

Deleted statement that maximum number of biopsy passes is 4. The maximum number of passes will be determined by treating physicians based upon considerations of safety.

Blood Sample

For those patients who do not co-enroll into LCCC1108, we will ask for a blood sample (~8mLs) to ensure sufficient germline DNA in the event tissue samples are insufficient. This change is reflected in section 1.6, section 6, 6.2 and 6.8

Management and Dose Modifications (section 4.4)

Deleted 'interstitial lung disease' as safety issues mostly for pneumonitis

Updated information on management based on most recent template language from GSK (section 4.4.3.1 on hypertension; 4.4.1.1 table on rash; 4.4.2 malignancies, 4.4.3.2 table on QTc prolongation; 4.4.3.3 reduced LVEF; 4.4.4 visual changes; section 4.4.5 pneumonitis; section 4.4.6 renal insufficiency; 4.4.7 diarrhea; 4.4.8 pyrexia; 4.4.9.1 (liver chemistry stopping criteria) and added sections on new primary melanoma (4.4.2.2) non-cutaneous malignancies (4.4.2.3), pancreatitis (4.4.10) and hyperglycemia (4.4.11). Updated section 4.4.12 (non-specific toxicities attributable to drug therapy)

Concomitant Medications (section 4.5)

Added investigational drugs to the list of prohibited medications, and added section 4.5.3 on dabrafenib and radiation.

Time and Events Table

In footnotes to table (section 6.1) clarified biopsy timing and timing of tumor imaging. At recommendation of manufacturer, added additional ophthalmic exams at cycles 2, 8 and annually thereafter. Regardless of progression/non-progression, clarified that patients will be evaluated (receive mandated study assessments) every 2 cycles or 6 weeks after cycle 9. (sections 6.1, 6.3 and 6.3.5) Consolidated study assessments. Widened study window for lab screening assessments to within 21 days prior to therapy initiation. Widened study windows for cycle 9 and beyond to +/-5 days.

Safety reporting

Included information on trametinib overdose (section 5.1)

Added new toxicities that should be reported as an SAE (section 7.1)

Glaxo fax number updated: [contact]

Appendix B: updated list of prohibited medications

Appendix G added: Ophthalmic Exam Worksheet for documentation of exam findings.

Appendix H added: safety information from ongoing randomized Phase 3 trial

THE ATTACHED VERSION DATED NOVEMBER 23 2014, INCORPORATES THE ABOVE REVISIONS

ATTACH TO THE FRONT OF EVERY COPY OF PROTOCOL

PROTOCOL AMENDMENT # 1

LCCC 1128: Open Label phase II trial of the BRAF inhibitor (Dabrafenib) and the MEK inhibitor (Trametinib) in Unresectable Stage III and Stage IV BRAF Mutant Melanoma; Correlation of Resistance with the Kinome and Functional Mutations

AMENDMENT INCORPORATES (check all that apply):

- X Editorial, administrative changes
- X_ Scientific changes (IRB approval)
- ___ Therapy changes (IRB approval)
- X_ Eligibility Changes (IRB approval)

The main driver for this amendment was to increase the window of time for screening for all but the laboratory evaluations and baseline tumor biopsy from 1 week to 3 weeks, to expand/reorganize the T&E table so that we each study visit for the first 6 months is included in the table, to clarify the timing of the biopsies at progression, and to include specific information for affiliate sites as the study is changing to multicenter. These changes are reflected in sections 4.2, 6.0 (Time and Events table), and sections 6.2-6.7.

In addition, the 2 medications included in the study were FDA approved as of May 2013, and this information has been incorporated into the study. These changes are reflected in sections 1.1, 1.3, and 1.4.

Safety and drug interaction information: Since this trial was initially approved in 2012, new IBs for each individual agent were issued by the manufacturer. In addition, a new IB for the combination of trametinib and dabrafenib was issued in May of 2013. Updated safety information (including drug interaction information) from each of these documents was incorporated into the protocol. These changes are reflected in sections 1.4.1, 1.5, 4.4.2.2., 4.4.3, 4.4.4, 4.4.7, 4.5.2, 5.1.5, 5.2.5, 5.2.7, and 5.2.8, and Appendix C section 11.3.

Eligibility

Section 3.1.7 was revised to indicate that the pre-treatment biopsy required by the protocol should not be performed until all other eligibility criteria are confirmed.

Section 3.1.8: females of child-bearing potential must continue effective contraception until 16 (not 4 weeks) post the last dose of study medication. Men with a female partner of childbearing potential must agree to effective contraception from D1 of study treatment (not 14 days prior to D1 as written previously).

Biopsies:

Section 4.2, Time and Events footnote 11, and sections 6.4, 6.7.: These sections were revised to indicate that tissue at baseline does not have to be from the original diagnostic specimen, but from any site. If tissue is not available, a core biopsy can be obtained from any site, not restricted to target lesions. Repeat biopsies were already required at progression. However, the timing was clarified with amendment #1 to indicate they should be performed within 7 business days of documented progression, and optimally within 4 hours of that day's study medication. Post-treatment biopsies will be not required for patients removed from the study for reasons other than

disease progression. Sections 4.1, 4.2, 6.4 and 6.7 were revised to indicate that patients will be requested to stay on study medication until the post progression biopsy is performed.

Section 6.9.3 Evaluation of Target lesions:

A note was added to this section **NOTE:** Whenever possible, a biopsied lesion should not be considered a target lesion for RECIST tumor assessments. If the biopsied lesion is the only site of measurable disease, it may only be followed as a target lesion if a core biopsy was performed. Lesions that have been completely removed or subjected to excisional biopsy should not be followed as target lesions.

Time and Events:

In addition to the logistical changes and details on biopsies noted above, the footnotes were revised to specify that the end of treatment visit should be performed 30 days after the last dose of study medication, and to allow dermatologic evaluations to be performed at an MD office local to the patient if the patient is not scheduled to come to the clinic. It was also emphasized that a scan of the brain is not required post-baseline unless clinically indicated.

In addition, the following editorial changes were made:

The PI was changed from [name] to [name] [name]. [name] remains as a co-investigator.

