4.2 Biopsies

At baseline, if patient does not have frozen tissue available (see section 6.6) fresh tissue must be obtained. If possible, the pre-treatment biopsy should be performed after all other eligibility criteria are confirmed. Enough tissue will be collected for both kinomining and NextGen sequencing if available (see section 6.6). Fresh tissue collection of accessible tumor will be repeated **at progression (clinical or radiological)** whether patient continues treatment post progression or

not. In fact, patients will be requested to remain on study medication until the biopsy at progression is performed. For subjects who are withdrawn from study treatment, but are later placed back on the trametinib/dabrafenib combination therapy, a biopsy may be collected from the former study subject at the time of progression from the standard of care trametinib/dabrafenib therapy. These subjects must be consented and placed back on study to allow for attainment of a biopsy at progression. These subjects will then remain on study for safety monitoring, in relation to the biopsy procedure, for 30 days. Subjects who have an ongoing \geq grade 2 or serious AE (SAE) related to the study procedure at 30 days will continue to be followed until the event is resolved or deemed irreversible by the investigator.

If possible, biopsies at progression should be performed within 7 business days of documented disease progression, and optimally within 4 hours of taking that day's study medication. If treating physician decides to continue treatment because the patient exhibits continued clinical benefit from therapy (and the patient agrees) then the biopsy can be delayed until the investigator deems the biopsy feasible as long as patient safety is not compromised. Post-treatment biopsies will not be required for patients removed for reasons other than disease progression; although, as mentioned above, if these subjects then go on to eventually receive the trametinib/dabrafenib combination in the future, as part of their standard of care, of the subject may be re-consented at the time of disease progression. See section 6.6 and laboratory manual. Please also see the note in section 6.9.3 regarding assessment of biopsied lesions per RECIST v1.1.

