6.7 Correlative Study Procedures

For both those patients who do and do not co-enroll into LCCC1108, we will ask for a blood sample (~8mLs in a yellow-top ACD tube) to ensure sufficient germline DNA in the event tissue samples are insufficient. This request and collection may take place at any point during the study, including during follow-up.

At baseline, if patient does not have frozen tissue available, fresh tissue must be obtained by biopsy. Biopsy of tumor will be repeated at or after progression (clinical or radiological) whether patient continues treatment post progression or not. If possible, biopsies at progression should be performed within 7 business days of documented disease progression, and optimally within 4 hours of taking that day's study medication. Please note that drug may be extended post progression (see section 4.1), and there is no need to hold drug for any length of time prior to the biopsy. In fact, patients will be requested to remain on study medication until the biopsy at progression is performed. If the treating physician decides to continue treatment at progression because the patient exhibits continued clinical benefit from therapy, the biopsy may be delayed until the investigator deems the biopsy feasible as long as patient safety is not compromised. Post-treatment biopsies will not be required for patients removed for reasons other than disease progression. See laboratory manual.

Note: For subjects who are withdrawn from study treatment, but are later placed back on the trametinib/dabrafenib combination therapy, a biopsy may be collected from the former study subject at the time of progression from the standard of care trametinib/dabrafenib therapy. These subjects must be re-consented and placed back on study to allow for attainment of a biopsy at progression.

Biopsies may be obtained by punch biopsy, core biopsy, or surgical excision, and may be performed by clinical personnel trained to do biopsies for standard of care collections. The number of - passes made through tumor per biopsy will be determined by the treating physician and the physician performing the biopsy procedure with primary consideration being safety. The tissue collected will be divided into aliquots (depending on size of collection, up to 4 aliquots per collection). For patients who co-enroll into LCCC1108 for NextGen sequencing, enough tissue will be collected for both kinomining and NextGen sequencing by

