6.7.1 Biopsy Risks

The risks of these procedures are associated with a small risk of pain, bleeding, infection, and damage to adjacent organs. The magnitude of this risk depends somewhat upon the site of the procedure.

Potential risks according to site are:

Skin/chest wall (punch biopsy or surgical excision):

Likely: local discomfort and minor bleeding.

Less likely: moderate or major bleeding, or infection

Lymph node or soft tissue (punch biopsy or surgical excision):

Likely: local discomfort and minor bleeding.

Less likely: moderate or major bleeding, need for blood transfusion, hospitalization due to bleeding or other complications, infection, pneumothorax, damage to adjacent organs. Additional risks may be present if intravenous conscious sedation (IVCS) is required (see below).

Liver (core needle biopsy):

Likely: local discomfort and minor bleeding

Less likely: moderate or major bleeding, need for blood transfusion, hospitalization due to bleeding or other complications, infection, bowel perforation or damage to adjacent organs

Additional risks may be present if IVCS is required (see below).

Breast (core biopsy): punch biopsy or surgical excision

Likely: local discomfort and minor bleeding.

Less likely: moderate or major bleeding, need for blood transfusion, hospitalization due to bleeding or other complications, infection, pneumothorax, damage to adjacent organs.

In order to minimize the risk of a biopsy, only qualified personnel will perform these procedures. Prior to the procedure, the physician performing the procedure will discuss the risks with each study participant, answer any questions, and obtain a separate procedure consent. For biopsies of lesions that are not superficial and clearly palpable, imaging studies such as CT or ultrasound will be

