6.9 Assessment of Primary Endpoint and Efficacy

Provided sufficient tumor tissue is available pre and post treatment (specifically at progression) to perform kinomining, data from the patient will be utilized to inform the primary objective. If a patient drops out of the study prior to progression, they may be replaced. See section 4.9 for additional information. For subjects who are withdrawn from study treatment, but are later placed back on the trametinib/dabrafenib combination therapy, a biopsy may be collected from the former study subject at the time of progression from the standard of care trametinib/dabrafenib therapy. Information from these biopsies will be included in the analysis of the primary objective and the correlative secondary objective.

Patients who have received at least 2 cycles of therapy and have their disease re-evaluated after 2 cycles will be evaluable for assessment of objective response. Patients who drop out of the study prior to this point will not be evaluable for response unless their disease progressed prior to this point.

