8.0 STATISTICAL CONSIDERATIONS

8.1 Sample Size and Data Analysis Plans

Our sample size justification is based on the primary objective to identify kinases which are differentially expressed between pre (just prior to treatment initiation) and post treatment (patients who developed resistance) after treatment with BRAF+MEK inhibition in melanoma patients.

The kinases will be profiled using Multiplexed Inhibitor Beads (MIBs) coupled with mass spectrometry. We anticipate this technique to capture between 50 – 100 kinases in melanoma patients. The kinase activity is reported as a quant ratio between the experimental and control samples. The Paragon algorithm[10] automatically identifies high confidence peptides that will contribute to the average quant ratio of a kinase. Our sample size justification is based on our ability to detect a meaningful difference in the kinase activity between pre and post treatment. The inherent matching of tumor by patient source pre and post treatment will provide a potential source of positive correlation that may be exploited to improve statistical power (e.g., using a paired t-test). However, in order to be conservative, we compute our statistical power using a two-tailed independent Mann-Whitney test in which the kinase activity is compared in the two groups. Based on preliminary data, we assume that 100 kinases are captured, of which 10% of them are truly differentially expressed between pre and post treatment and a common standard deviation of 0.95 (in \log_2 scale).

Table 1 summarizes the power to detect a true difference of D with a sample size of 20 tumors in each group (pre and post treatment) at FDR of 0.05 to account for multiple testings. For example, we achieve a power of 0.92 to detect a \log_2 difference of 1.32 (or a fold change of 2.5) for each kinase between pre and post treatment.

D=Difference in \log_2 scale	1.00	1.32	1.58	1.81
Fold change (2^D)	2	2.5	3	3.5
Power	0.59	0.92	0.99	1.00

Data Analysis Plans

Exploratory tools such as heatmaps and two-way unsupervised hierarchical clustering will be utilized as visual representation of overall kinome activity. The

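### Baseline and progression biopsies may come from different tissue types and 8.1 has no tissue term, so a one-directional shift in tissue mix could enter the primary kinase list unseen

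*Combined protocol and SAP*

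**What the plan says.** **Baseline.** The operative text is footnote 13 in 6.1: fresh tissue is needed only if no frozen tissue exists from any site of disease. The summary of Amendment #1 shows where this came from: "tissue at baseline does not have to be from the original diagnostic specimen, but from any site". Sections 4.2 and 6.7 do not repeat it. Schema note a in 4.1 and the tissue paragraph of 6.2 still tie frozen tissue to the diagnostic specimen or biopsy, so the current text is not uniform.

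**Progression.** Section 4.2 states: "Fresh tissue collection of accessible tumor will be repeated". Footnote 13 and 6.7 ask for no more. No section asks for the same lesion, organ or tissue class. Section 6.7 adds: "Biopsies may be obtained by punch biopsy, core biopsy, or surgical excision". An excised lesion cannot be sampled again. The risk list in 6.7.1 covers skin or chest wall, lymph node or soft tissue, liver and breast.

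**Analysis.** Under 6.9 a patient informs the primary objective on one condition: "Provided sufficient tumor tissue is available pre and post treatment (specifically at progression) to perform kinomining". Section 8.1 refers to pairing only by patient: "The inherent matching of tumor by patient source pre and post treatment will provide a potential source of positive correlation". It plans a univariate comparison per kinase with FDR adjustment, nearest shrunken centroids, clustering and kinase sets. It names no tissue covariate, stratum, restriction or sensitivity analysis. Off-study progression biopsies are pooled into the same data set.

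**The concern.** The primary endpoint (2.3) is the pre/post kinome comparison, in a single arm. A biopsy carries some of the organ around the tumor. If one sample of a pair is nodal and the other hepatic or cutaneous, lymphoid, liver or skin kinases differ for reasons unrelated to treatment. Pairing by patient removes stable differences between patients, but not a difference in organ within the pair. With no control arm, nothing in the design would reveal such a shift. A tissue kinase that passes the FDR filter would be reported as a marker of resistance.

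**Working it through.** **Inputs from 8.1.** 20 tumors per group, 100 kinases of which 10% truly change, SD 0.95 (log2), FDR 0.05.

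**The plan's own figure.** Per-test alpha and power are solved jointly: alpha* = m1·power·f / [m0·(1 − f)], with m1 = 10, m0 = 90, f = 0.05. At D = 1.32, alpha* = 10 × 0.916 × 0.05 / (90 × 0.95) = 0.0054. A two-sample t-test then gives power 0.585 / 0.916 / 0.987 / 0.998 for D = 1.00 / 1.32 / 1.58 / 1.81. Table 1 states 0.59 / 0.92 / 0.99 / 1.00, so the inputs are understood.

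**Assumed, because the documents are silent.** 15 kinases differ by d log2 units between two tissues; k of 20 pairs change tissue; within-pair correlation ρ is 0 to 0.5; there is no true treatment effect. Every declared kinase is then false, and FDR 0.05 should give at least one in about 5% of trials.

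**Why direction matters.** If all k mismatches run one way, the mean shift in a tissue kinase is d·k/20. Its standard error is about √{[2(1 − ρ)·0.95² + d²(k/20)(1 − k/20)]/20}. For d = 2, k = 10, ρ = 0.5 the shift is 1.0, the SE is √[(0.9025 + 1)/20] = 0.308, and the ratio is 3.2. If mismatches split evenly, the shift is 0 and only the added variance remains.

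| Mismatch (paired t) | d | Mean shift | Shift/SE, ρ = 0 to 0.5 | Simulated chance of ≥1 false kinase |
|---|---|---|---|---|
| Balanced | 1 or 2 | 0 | 0 | about 2–6% |
| 8/20 one way | 1 | 0.4 | 1.3 to 1.7 | about 15–21% |
| 10/20 one way | 1 | 0.5 | 1.6 to 2.1 | about 23–44% |
| 5/20 one way | 2 | 0.5 | 1.4 to 1.7 | about 10–13% |
| 8/20 one way | 2 | 0.8 | 2.2 to 2.6 | about 35–54% |
| 10/20 one way | 2 | 1.0 | 2.7 to 3.2 | about 77–97% |

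Section 8.1 does not name the test for the final analysis. The unpaired Mann-Whitney test used for power is less affected: at d = 2, about 5–28% (8/20) and 29–63% (10/20). Here the lower ends belong to the higher correlation, which that test ignores.

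**Second check, with true effects present.** 10 true kinases at D = 1.32, 20 tissue kinases, Mann-Whitney. Realised FDR by share of samples from the second organ, pre to post, at d = 1 and d = 2:
- 30% to 30%: 0.03, 0.04
- 20% to 50%: 0.07, 0.14
- 0% to 50%: 0.15, 0.41
- 20% to 80%: 0.26, 0.55
- 0% to 100%: 0.61, 0.69

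An unadjusted paired t-test gives nearly the same at 20% to 80% (0.26, 0.52). Regressing the paired difference on the signed change of site returns FDR to about 0.04–0.06, except in the last mix, where tissue and time cannot be separated.

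**What adjustment costs.** Regress post minus pre on z, where z is +1, 0 or −1 for the direction of tissue change. Relative to the unadjusted mean, and at equal residual variance, the intercept's SE is multiplied by √[1 + 20·z̄²/Σ(z − z̄)²].
- 8 one way: z̄ = 0.4, Σ = 8 − 20 × 0.16 = 4.8, factor √(1 + 3.2/4.8) = √(20/12) = 1.29. Power at D = 1.32 is about 0.5 against 0.87 (ρ = 0), or 0.92 against about 1.0 (ρ = 0.5).
- 4 each way: z̄ = 0, factor 1. With a 30% to 30% random mix and no within-pair correlation, power is 0.83 adjusted and 0.86 unadjusted.
- An unsigned any-change indicator: the intercept is the mean of the 12 same-tissue pairs, so the 1.29 is paid even when mismatches balance and there is no bias to remove.
- All 20 one way: Σ = 0, and tissue and time cannot be separated.

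**The case against.** Nothing in the documents says that the tissue mix shifts between baseline and progression. Section 6.7.1 is a list of procedural risks by site, not a forecast of where biopsies will be taken. The large figures need 8 to 10 of 20 pairs mismatched the same way and a 4-fold tissue effect in 15% of kinases. The study is described as exploratory, and an adjusted analysis used as a hurdle could nearly halve power. Tissue handling is deferred to a laboratory manual that is not available here and may already capture the organ. All of this stands. It limits the size of the point and shapes the remedy, but it does not supply the missing tissue term in 8.1.

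A reader might infer three stronger things that the documents do not support:
- That pairs will differ by organ. The text permits this by silence and does not state it.
- That any mismatch produces false resistance kinases. Balanced mismatch leaves the error rate nominal.
- That the sample size depends on a gain from pairing which mismatch would erode. Section 8.1 mentions pairing as a possible benefit, but computes power with an independent-groups test precisely to avoid relying on it.

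**Conclusion.** The gap is real and modest. The current text allows baseline and progression tissue to differ in type, and 8.1 neither adjusts for this nor checks it. Whether it does harm depends on a one-directional shift that the documents neither show nor rule out. Under the stated assumptions the chance of at least one false kinase with a paired t-test runs from nominal (2–6%, balanced) through about 10–21% (5/20 at 2 log2, or 8/20 at 1 log2) to 77–97% (10/20 at 2 log2). The tissue effect, the number of tissue kinases and the site mix are all assumptions. This is a low-cost improvement that protects the interpretation of the primary list; it is not evidence that the planned analysis will fail.

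**What to change.** **Sections 4.2 and 6.7.** When more than one progressing lesion can be biopsied equally safely, prefer the one in the same tissue class as the baseline sample (skin or soft tissue, lymph node, viscera). Record the organ of every sample, including off-study progression biopsies, if this is not already captured. Align schema note a and 6.2 with footnote 13 on which frozen tissue is acceptable.

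**Section 8.1.** Keep the planned analysis and add a prespecified sensitivity analysis with a signed tissue term: the tissue-class indicators of the post sample minus those of the pre sample, or equivalently a model with patient, time and tissue class. Report with each named kinase whether its estimate holds after adjustment. Do not make adjustment a condition for naming a kinase, and do not use an unsigned any-change indicator.

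**Cost.** A few sentences and at most one eCRF field, with no extra biopsy. Where mismatches run one way, the adjusted estimates are less precise, so failure to hold after adjustment is weak evidence against a kinase. If every pair changes tissue in the same direction, no model can separate tissue from time, which is why the same-class preference at biopsy matters.
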